### **6.3.5 Pharmacokinetic Analysis**

No pharmacokinetic analysis is needed in this medical device Study.

### **6.3.6 Safety Analysis**

All Subjects entering the Study will be included in the safety analysis. Clinical Patient Assessment Measurements (i.e., pain, feeding tolerance, and usual measures to determine EAD(P) location) will be performed prior to, immediately following, and for up to three (3) days after all Interventions. Clinically significant changes will be addressed and managed by the Subject's medical team, but recorded, reported, and followed by the Study team. Surveillance will include assessment for any adverse event(s) related to the intervention (i.e. EAD(P) displacement, EAD(P) damage, enteral tract tissue injury) and will continue for up to three (3) days following interventions in either group. Patients who are discharged from the hospital prior to three days will be followed up daily by phone for Clinical Assessment Measurements i.e., pain, feeding tolerance and EAD(P) location as assessed by caregiver until post intervention day three.

## **6.4 Sample Size and Power**

[figure not shown]
Sample size has been selected such that the power ( $1 - \beta$ ) of primary endpoints is  $1 - \beta \geq 0.8$ , with  $\alpha = 0.05$ .

- The efficacy of TubeClear® is expected to be at least 95% based on previous bench testingxi. The efficacy of CHOP Standard Treatment is expected to be about 50% based on focus group conclusions.xii Sample size results, displayed graphically, are as follows:

---

xi TP-5007-079 and TR-5007-079

xii Conclusions of Clinician Focus Groups, July 2009

**Figure 9: Sample size as a function of power at three different alpha levels**

To ensure proper power is achieved a sample size of 17 Subjects in each group is needed (**Figure 9**).

- The efficiency of TubeClear® (Intervention time of TubeClear® to the CHOP Standard Treatment) is expected to be at least one standard deviation (40 minute difference of average time, 0.243 minute standard deviationxiii) greater than that of CHOP Standard Treatment based on bench testing.xiv Therefore, a sample size of 17 in each group is more than sufficient to show statistical significance of the desired effect.

## 6.5 Interim Analysis

No interim analysis will be performed. Phase I results will be complied into a report and submitted to the IRB for review. Continuation into Phases IIA and IIB will be determined by the IRB based on the reported results of Phase I.

xiii40 minute difference = 42.8 minute average time for Standard Treatment – 2.8 minute average time for tube clear (data from section 1.1, **Table 2** of protocol). 0.243 standard deviation is calculated from data in TR-5007-079.

xiv TR-5007-079

## 7 STUDY DEVICE

### 7.1 Description

TubeClear® is the investigational device. TubeClear® is intended to clear the occlusions in EAD(P)s. TubeClear® is comprised of a reusable Control Box and a single use Clearing Stem. TubeClear® is currently FDA cleared for use ONLY and SOLELY in clearing occlusions/clogs from EAD(A)s. Clearing Stem models for ND, NG, NJ, G, and J Tubes of size 10 – 18 Fr, 10 – 140 cm and ND, NG, NJ, G, and J Tubes of size 6 – 18 Fr, 15 – 36 cm for adults have been FDA cleared (Appendices A-E). The FDA has deemed TubeClear® to be non-significant risk for use in this study (Appendix D).

This Study evaluates the use of TubeClear® in pediatric patients for the restoration of EAD(P) patency. The Clearing Stems being evaluated in this Study will be used with Pediatric Enteral Access Device ND, NG, and NJ 6 – 8 Fr, 38 – 140 cm; NG tube (Corflo, Corpak MedSystems) used as a jejunal tube inserted through a gastrostomy tube, 6 – 8 Fr, 38 – 140 cm; and AMT GJ tube, 14 Fr, 38 – 140 cm (15 – 55 in).

TubeClear® use will be compared to the CHOP Standard Treatment for restoring patency in occluded EAD(P) by efficacy and TubeClear® related adverse events will be monitored and reported. CHOP Standard Treatment administration during this Study will follow standard protocol at CHOP.

#### 7.1.1 Packaging

TubeClear® is comprised of a reusable Control Box and a single use Clearing Stem. Both the Control Box and Clearing Stem are non-sterile. The Control Box can be stored in a custom carrying case or mounted to an IV pole. The exterior surfaces of the Control Box are to be wiped between uses with the disinfectant method used as part of CHOP's standard procedure for medical equipment that enters a patient's room. The Clearing Stems are disposable (for one-time use only) and individually packaged in a sealed bag. Each sealed bag contains a Clearing Stem and Directions for Use. The Directions for Use are a reference for using TubeClear® but do not replace the need to read, understand, and follow the TubeClear® Operator's Manual (i.e., Instructions for Use).

#### 7.1.2 Labeling

TubeClear® Control Box is packaged with an Operator's Manual. Operators are responsible for reading, understanding, and following the Operator's Manual. Each Clearing Stem bag is labeled for the specific Clearing Stem Model, including EAD type, Fr size, Clearing Stem Model number, Clearing Stem Model color, intended use, cautions, and warnings.

#### 7.1.3 Dosing

TubeClear® does not require dosing. In this Study, the Investigator will determine the EAD(P) length by Subjects chart or markings on the EAD(P). The Investigator will place the Operator-set Collar on the Clearing Stem to the centimeter marking that corresponds with the HER

and/or markings on the EAD(P). CHOP Standard Treatment will be administered according to CHOP standard protocol.

#### **7.1.4 Treatment Compliance and Adherence**

The Study intervention does not require ongoing treatments. Therefore, no compliance or adherence to ongoing treatment is needed.

#### **7.1.5 Device Accountability**

Records of the Study device (TubeClear®), and its disposition will be maintained by the Study Coordinator. These records will include device reception, device supply orders, device dispensing records, and disposition forms (in addition to model number and any other identifying information on the individual Clearing Stem). These records will be examined during the course of the Study by the Investigators and the Study Sponsor. The purpose of these records is to ensure to regulatory authorities and the Sponsor that the investigational device will not be distributed to any person who is not a Study Subject under the terms and conditions set forth in this protocol. At Study completion, all device supplies, including partially used and empty containers, must be returned to the Study Sponsor with the exception of the used Clearing Stems.

## 8 SAFETY MANAGEMENT

### 8.1 Clinical Adverse Events

Clinical adverse events (AEs) (any unfavorable and unintended sign including an abnormal finding, symptom or disease associated with the use of a medical intervention, regardless of whether it is considered related to the medical intervention, that occurs during the course of the Study) will be monitored throughout the Study. While no clinical adverse events are anticipated, potential adverse events include:

- Clearing Stem exits the distal end of the EAD(P) and punctures the intestinal mucosal membrane.
- Clearing Stem causes damage to the EAD(P) that requires replacement of the EAD(P).
- A possible clinical adverse event for either intervention would be that the occluded medication is bolus flushed into the Subject's digestive system when patency is restored. The medication will have a varying rate of absorption in the digestive system that may cause unanticipated side effects to the Subject depending on the medication's safe therapeutic range. However, when using the TubeClear® occlusion clearing procedure (**Figure 4**) (i.e., an iterative process of partially clearing the occlusion then aspirating the broken occlusion particles, repeating until the collar reaches the EAD external ports (**Figure 2B**) would minimize potential for this clinical adverse event. Since the medication is periodically aspirated from the EAD(P), the final EAD(P) patency flush should contain minimal medication.
- The contrast used in the post-intervention radiograph could result in an allergic reaction to contrast agent. The post-intervention radiograph will also incur a dose of radiation. However, this dose replaces the dose that would be received for EAD(P) replacement if the occlusion was not cleared.

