## 5 STUDY EVALUATIONS AND MEASUREMENTS

### 5.1 Screening and Monitoring Evaluations and Measurements

#### 5.1.1 Medical Record Review

Information from the medical record will be recorded and used for this study. This information will include medical history, information about your condition, lab and radiology results, medications, treatments, vital signs, and the response to treatments. We will be reviewing the medical record throughout the study.

We plan to follow-up all subjects for 3 days post-intervention in all study phases. It is possible that some study subjects might be discharged from the hospital prior to this endpoint. In such instances, we will need to contact the parent/guardian of the subject (as third party and not part of research procedures) and administer the follow-up questionnaire on a daily basis (till post-intervention day 3). As we cannot predict which subject is likely to be discharged prior to 3 days, we will obtain contact information for parents/guardians of all subjects at the time of obtaining informed consent.

Variables that will be abstracted from the EHR will include the following.

- Basic demographic information including subject name, medical record number (MRN), account number (CSN), Date of birth (DOB), race, ethnicity, sex, age at time of Study Intervention, weight, stature, calculated BMI, location (PICU/PCU/IR) and dates of hospitalization (length of stay)
- Contact information of parent/guardian will be collected to follow-up subjects for study related events, (in case subject is discharged prior to post-intervention day 3)
- Type of EAD(P)
- Date and place of EAD(P) insertion
- Length of EAD(P)
- EAD clog information
- Medications
- Nutrition
- Diagnoses
- Procedures
- Severity of illness
- Ventilator parameters (if applicable)
- Medications administered through EAD(P) preceding clog

- Nutrition administered through EAD(P) preceding clog
- Past Medical History
- Past Surgical History
- Established age-appropriate pain scales
- Laboratory results and radiology results

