### 6.3.3 Primary Objective Analysis

Data from Phase I and Phase IIA will be observational and will not test a hypothesis. Data on feasibility and tolerability from Phase I and data on EAD(P) patency restoration will be reported as counts and percentages.

In Phase IIB, the primary objective is efficacy comparison between TubeClear® intervention and CHOP Standard Treatment. EAD(P) patency restoration will be measured by the ability to flush the EAD(P) with 10 ml of air within five (5) minutes following the Intervention. Efficacy is the proportion of EAD(P)s restored to patency in each group. A chi-square analysis (or Fisher's exact test) will be performed to compare the efficacy of TubeClear® intervention to the CHOP Standard Treatment. Intention-to-treat analysis will be used to compare the efficacy of the TubeClear® intervention to the CHOP Standard Treatment. Patients will be analyzed according to their randomized allocation. Full reporting of any deviations from random allocation and missing responses will be recorded and assessed in accordance with the CONSORT guidelines. Exploratory-per-protocol analysis will also be reported.

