#### **6.3.4 Secondary Objective Analysis**

Data from Phase I and Phase IIA will be observational and will not test a hypothesis. Data on 1) pain, using established age-appropriate pain scales, 2) physiologic changes in vital signs, 3) distress related EAD(P) events, and 4) adverse events related to TubeClear® use will be described and reported as counts and percentages.

In Phase IIB, the secondary objectives between TubeClear® intervention and CHOP Standard Treatment include comparison of 1) time to intervention, 2) pain using established age-appropriate pain scales, 3) physiologic changes in vital signs, 4) distress related EAD(P) events, and 5) adverse events related to either group.

1. A log-rank test will be performed to compare intervention time of TubeClear® intervention to the CHOP Standard Treatment.
2. A Wilcoxon rank sum test will be performed to compare differences in subject pain and discomfort between TubeClear® intervention and CHOP Standard Treatment.
3. A t-test will be performed if the distributions are normal (or non-parametric equivalent, if the distributions are not normal) to compare differences in physiologic changes (i.e. vital sign changes) between TubeClear® intervention and CHOP Standard Treatment.
4. A Wilcoxon rank sum test will be performed to compare differences in distress related EAD(P) events (i.e. subject behavior such as pulling/yanking) between TubeClear® intervention and CHOP Standard Treatment.
5. A chi-square analysis (or Fisher's exact test) will be performed to compare the proportions of adverse events (i.e., EAD(P) displacement from the intervention; EAD(P) damage from the intervention; any enteral tract tissue perforation from the intervention) in TubeClear® intervention and CHOP Standard Treatment.

Intention-to-treat analysis will be used to compare the secondary endpoints between the TubeClear® intervention and the CHOP Standard Treatment. Patients will be analyzed according to their randomized allocation. Full reporting of any deviations from random allocation and missing responses will be recorded and assessed in accordance with the CONSORT guidelines. Exploratory-per-protocol analysis will also be reported.

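### Section 8.1 names a medication bolus and a contrast reaction as possible harms, but no planned Phase IIB summary by arm includes either

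*Combined protocol and SAP*

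**What the plan says.** Section 8.1 lists potential adverse events. One is systemic and applies to both arms: "A possible clinical adverse event for either intervention would be that the occluded medication is bolus flushed into the" digestive system when patency returns, with effects that depend on the drug. The same bullet says that TubeClear's repeated aspiration should keep this risk to a minimum. A further bullet names an allergic reaction to the contrast used for the post-intervention film.

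The analysis sections are narrower:

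- Section 6.3.4 first lists adverse events in either group as a Phase IIB secondary comparison. Item 5 then defines the test as one to "compare the proportions of adverse events (i.e., EAD(P) displacement from the intervention; EAD(P) damage from the intervention", with perforation of enteral tissue as the third and last event.
- Section 6.2 has incidence reported in both Phase IIB groups, again only for displacement, damage and tissue injury.
- Section 6.3.6 includes everyone who enters the study in the safety analysis, but specifies no by-arm table. It says: "Surveillance will include assessment for any adverse event(s) related to the intervention (i.e. EAD(P) displacement, EAD(P) damage, enteral tract tissue injury".

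Collection is broader. Section 5.4 monitors any unwanted event, stores a description of each in the study database, and has it classified for severity, expectedness and relatedness. Section 5.1.1 abstracts "Medications administered through EAD(P) preceding clog", but no safety analysis uses that field.

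**The concern.** A safety comparison should at least cover the harms that the protocol itself foresees. Here the by-arm comparison is confined to tube and tissue events, so a drug effect or a contrast reaction could be recorded and still appear in no planned summary by arm. Section 8.1 also makes what is in effect a comparative safety statement about the device: that its clearing procedure limits the bolus. No clinical figure is cited for this, and no planned analysis looks at it. Section 9.5 says that the data may support a premarket notification.

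The denominator matters too. A bolus of this kind can occur only when a tube opens, and the plan expects the two arms to differ greatly in how many tubes open. A reader of the results will need to know both how many events occurred and out of how many opened tubes.

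**Working it through.** **Inputs (6.4 and 6.3.3).** "The efficacy of TubeClear® is expected to be at least 95% based on previous bench testing"; "The efficacy of CHOP Standard Treatment is expected to be about 50% based on focus group conclusions"; "a sample size of 17 Subjects in each group is needed". The power target is at least 0.80 at alpha 0.05. The primary test: "A chi-square analysis (or Fisher's exact test) will be performed to compare the efficacy". The readable text does not state whether the test is one- or two-sided.

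**The plan's own figure.** Full enumeration of the two-sided Fisher test for 0.95 v 0.50 gives power 0.777 at 16 per arm and 0.813 at 17. The stated 17 reproduces exactly.

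**Step 1: tubes opened by the allocated intervention.** Expected number = n × expected patency rate.

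- TubeClear: 17 × 0.95 = 16.15
- Standard Treatment: 17 × 0.50 = 8.5
- Ratio: 16.15 / 8.5 = 1.90

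**Step 2: how firm the ratio is.**

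- *Other rates in the protocol.* Table 2 (30/30 v 29/30 for enzyme) gives 30/29 = 1.03. Figure 6 (14/15 v 5/15 for enzyme) gives 14/5 = 2.8.
- *Clog content.* If a share m of clogs contains medication, equal in both arms (assumed), the tubes at risk are 4.0 v 2.1 at m = 0.25, 8.1 v 4.3 at m = 0.5 and 12.1 v 6.4 at m = 0.75. The ratio stays 1.90 but the counts fall.
- *Later opening.* Tubes that the allocated intervention fails to open pass to the clinical team (4.2). If a share g of failures is then opened in place, equal in both arms (assumed), the ratio is (16.15 + 0.85g) / (8.5 + 8.5g): 1.90 at g = 0, 16.575/12.75 = 1.30 at g = 0.5, and 17/17 = 1.00 at g = 1.

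**Step 3: from tubes to events.** The documents give no bolus rate. With the same assumed risk per opened tube in both arms:

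| Risk per opened tube | Expected events, TubeClear v control |
|---|---|
| 5% | 0.81 v 0.43 |
| 10% | 1.62 v 0.85 |
| 20% | 3.23 v 1.70 |

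If aspiration cuts the TubeClear risk per opened tube to a fraction f of control (assumed), the event ratio is 1.9f: 1.43 at f = 0.75, 1.0 at f = 0.53 and 0.48 at f = 0.25. The direction therefore depends on an unknown.

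**Step 4: what a test could show.** Two-sided Fisher power at 17 per arm, with equal risk per opened tube:

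| Risk per opened tube | Risk per arm | Power |
|---|---|---|
| 10% | 9.5% v 5% | 0.8% |
| 20% | 19% v 10% | 4.5% |
| 30% | 28.5% v 15% | 8.1% |
| 50% | 47.5% v 25% | 17.2% |

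Even no events in 17 leaves a one-sided 95% upper limit of 1 − 0.05^(1/17) = 16.2%.

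**Step 5: the contrast denominator.** The abstract and sections 2.2, 4.2 and 6.2 give every subject a contrast film after either intervention. Section 5.4 ties it to successful restoration. At the planning rates these readings give 17 v 17 or about 16 v 8.5 exposed, so the passages must be reconciled before a rate is reported.

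**The case against.** The best case for the plan is that nothing is lost. Section 8.1 has adverse events monitored throughout the study whatever their cause, and lists the bolus directly beneath. Section 5.4 records every event. The abstract sends all of them to the IRB and medical monitor, and section 9.4.1 adds daily and monthly review. Section 6.3.4 item 3 compares vital-sign changes by arm, which could pick up some drug effects.

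Much of this stands. A reader might infer from the short surveillance lists that the bolus is not monitored at all. The general definitions in 5.4 and 8.1 rule that out. But recording and review are not a comparison by arm, and vital signs neither identify a drug effect nor connect it with what was in the clog.

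A reader might also infer from 16 v 8.5 that the harm would be about twice as common with TubeClear. The documents do not support that. The ratio counts tubes opened at planning rates, not events. It ignores clogs without medication, control tubes opened later, and the aspiration described in the same bullet.

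It is also fair to say that a formal test including the bolus would almost always be non-significant at this size, so leaving it out does not suppress a finding that the trial would otherwise have made.

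**Conclusion.** The point holds as a gap in prespecified reporting. Two potential harms named in 8.1 enter no planned Phase IIB summary by arm, because 6.3.4 item 5 and 6.2 define the events compared as tube and tissue events only. The expectation that the TubeClear procedure limits the bolus is left unexamined.

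The number at risk may differ by arm: about 16 v 8.5 tubes opened by the allocated intervention, if the 95% and 50% planning rates hold. No direction or size of excess harm can be claimed, since clog content, the effect of aspiration and later opening by the clinical team are all unknown. The primary efficacy analysis and the sample size are unaffected. The change is worth making because it costs little and brings the safety summary into line with the protocol's own list of harms.

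**What to change.** In 6.3.4 item 5 and 6.3.6, add descriptive rows by randomised arm, drawn from the 5.4 database, each per randomised enrolment (a child may be enrolled up to three times):

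- **(a) Any adverse event.**
- **(b) Suspected medication-bolus effects.** Show these also per restored tube as a supplementary figure, labelled as conditioned on a post-randomisation outcome that treatment itself affects. List each case with the medications given through the tube before the clog.
- **(c) Contrast reactions.** Show these also per subject actually given contrast, not per restored tube.

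Report the same rows for Phases I and IIA. Section 6.3.4 already promises counts and percentages of adverse events there, but does not name these categories.

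The cost is some analysis wording and a few table rows from fields already planned. The study team should write down in advance what counts as a suspected bolus effect, so that events are classified alike in both arms. The downside is very low counts: the rows should carry no hypothesis test, and an empty row should not be read as evidence of safety.

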### 8.2 Adverse Event Reporting

The Investigator is responsible for recording and reporting unanticipated problems related to research that occurs during and after the Study Intervention. The plan for AE reporting is consistent with CHOP IRB Guidelines.

Since TubeClear® is a non-significant risk device (**Appendix D**) in adults, serious adverse events (SAEs) are not expected. If any unanticipated problems related to the research involving risks to Subjects or others occur during the course of this Study (including SAEs), they will be reported to the IRB in accordance with CHOP IRB SOP 408: Unanticipated Problems Involving Risks to Subjects. AEs that are not serious but are notable and could involve risks to Subjects will be summarized in narrative or other format and submitted to the IRB at the time of continuing review.

## **9 STUDY ADMINISTRATION**

### **9.1 Treatment Assignment Methods**

#### **9.1.1 Randomization**

A randomization sequence will be generated by computer program by the Study Sponsor for the randomized efficacy comparison in Phase IIB. The Study Team will be responsible for maintenance and execution of randomization sequence. The randomization sequence will be kept in individual sealed envelopes to be opened after the Subject is consented and enrolled in the Study. To ensure an appropriate balance of participation in both the TubeClear® intervention and CHOP Standard Treatment Groups, balanced, permuted block randomization will be used, as the Study is not entirely blinded.

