In Phase IIB, subjects will be randomized into either TubeClear® intervention or CHOP Standard Treatment using a predetermined computer generated randomization sequence stored in opaque sealed envelopes. Prior to the intervention, the location of the EAD(P) will be determined based on review of radiographs. The Investigator may obtain a new radiograph if the EAD(P) location is uncertain. The Investigator will determine the length and diameter of the EAD(P) from the EHR and/or the length marking (in cm) at the exit point of the EAD(P) from the body surface orifice. If randomized to TubeClear®, the Operator-set Collar on the clearing stem of TubeClear® will be placed corresponding to the EAD(P) measured length recorded by the Investigator. The TubeClear® Instructions for Use (i.e., Operator's Manual) will be followed by the user to restore patency to the EAD(P). If randomized to CHOP Standard Treatment, the CHOP protocol to restore patency to occluded EAD(P) will be followed. EAD(P) patency restoration will be measured by the ability to flush the EAD(P) with 10 ml of air within five (5) minutes after completion of the intervention. After successful air flushing, aspirate will be extracted through the EAD(P), and the pH of the contents checked to confirm location according to CHOP standard of care. Following confirmation of correct EAD(P) placement, 5-20 ml of water will be flushed through the EAD to assure continued patency. Following either intervention, the Subject will receive an abdominal radiograph with contrast. A radiologist (blinded to the study) will assess the radiographs for adverse events (i.e., EAD(P) displacement, EAD(P) damage, enteral tract tissue injury) attributable to the intervention. If either intervention is unable to restore EAD(P) patency, further steps to restore patency of the occluded EAD will be determined by the clinical team per usual practice.

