## **3.2 Allocation to Treatment Groups and Blinding**

All Subjects in Phase I and Phase IIA of the Study will receive TubeClear® to restore patency of the occluded EAD(P).

All Subjects in Phase IIB will be randomized into the TubeClear® intervention (experimental) or CHOP Standard Treatment (control) group according to a predetermined computer generated randomization sequence. The randomization sequence will be kept in individual opaque sealed envelopes to be opened after the Subject is consented and enrolled in Phase IIB. To ensure an appropriate balance of participation in both the experimental and control groups, balanced, permuted block randomization will be used, as Phase IIB is not blinded.

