### **3.4.2 Exclusion Criteria**

1. Ward of the state
2. Positive pregnancy test/ Pregnant females
3. Any active gastrointestinal abnormalities or malformations, including but not limited to infections, inflammation, obstruction and/or recent abdominal surgery or trauma
4. Constant dependency on the EAD(P) for a glucose source (e.g. hyperinsulinism states)
5. Unable to tolerate water volume needed for the EAD(P) flush
6. Allergies to the contrast agent(s) used in post-Intervention radiological imaging
7. Measured total length of EAD(P) less than 38 cm (15 in) - from external port to EAD(P) distal end
8. Unknown length of EAD(P)
9. Attending physician declines enrollment based on clinical judgement
10. Subject attains 18 years of age during study duration

Subjects that do not meet all of the enrollment criteria will not be enrolled. Any violations of these criteria will be reported in accordance with IRB Policies and Procedures.

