#### **9.1.2 Blinding**

This Study will be blinded to the radiologist reading the abdominal radiographs post-intervention. The Study will not be blinded to the Investigators, Study Nurse, or other research staff due to the nature of the interventions in this Study.

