## **9.6 Recruitment Strategy**

Subjects will be recruited from patients in the CHOP PICU, PCU, and/or IR that are identified to have an occlusion of their EAD(P)s during the current admission. Potential eligible Subjects will be identified by screening the electronic health records (EHR). In addition, CHOP staff may notify the research personnel when there is a potential Subject. The Research Personnel will screen potential Subjects using the protocol inclusion and exclusion criteria. Information about this study will be disseminated electronically via email and described on the PICU website on the intranet.

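### Open-label Phase IIB uses permuted blocks of unstated size with no custodian independent of enrolment, so some upcoming allocations may be predictable before consent

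*Combined protocol and SAP*

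**What the plan says.** Generation, custody and concealment:

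- Section 9.1.1: "A randomization sequence will be generated by computer program by the Study Sponsor". The same section continues: "The Study Team will be responsible for maintenance and execution of randomization sequence".
- Section 3.2: "The randomization sequence will be kept in individual opaque sealed envelopes to be opened after the Subject is consented and enrolled in Phase IIB". Section 3.1.2 also describes a "predetermined computer generated randomization sequence stored in opaque sealed envelopes". Section 9.1.1 repeats the individual sealed envelopes and the timing, without the word opaque.
- Section 3.2, at the end of a sentence whose stated aim is balance between the arms: "balanced, permuted block randomization will be used, as Phase IIB is not blinded". No block size is given, nor whether it varies or is withheld from enrolling staff.

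Who knows and does what:

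- Section 9.1.2: "The Study will not be blinded to the Investigators, Study Nurse, or other research staff". Only the radiologist is blinded.
- Section 9.6: "The Research Personnel will screen potential Subjects using the protocol inclusion and exclusion criteria". Section 9.7 has the Investigator obtain consent.
- Section 3.4.2, item 9, excludes a patient if: "Attending physician declines enrollment based on clinical judgement". Items 7 and 8 exclude a tube shorter than 38 cm or of unknown length.

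Order of steps: the Phase IIB list in Section 4.2 puts randomization ahead of radiograph review, and mentions finding the tube length only for subjects allocated to TubeClear. Section 3.1.2 also mentions randomization first, but its sentence on tube length reads as applying to both arms.

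**The concern.** Balanced blocks in an open trial carry information. Once past allocations are known, the remaining places in a block of known size can be counted, and the last ones are certain. Lack of blinding is therefore a reason for caution with blocks, not a reason for using them.

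A guess about the next arm can affect whether a patient is approached, delayed or declined, all of which happens before any envelope is opened. If patients whose tubes look easier to clear enter more often when one arm is expected, the arms differ in a factor that drives patency. Intention-to-treat keeps subjects in their allocated arm but does not repair selection before allocation. The primary test in Section 6.3.3 is an unadjusted chi-square or Fisher comparison, and covariates are only exploratory (Section 6.3.2). The investigator also measures patency (Section 5.2).

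The order in Section 4.2 raises a related problem. If length is established after allocation, and in one arm only, an exclusion can be applied once the arm is known.

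**Working it through.** **1. The plan's own figure.** Inputs from Section 6.4: success 0.95 and 0.50, alpha 0.05, power at least 0.80, 17 per arm. I summed the binomial probabilities of all tables with two-sided Fisher p ≤ 0.05. Power is 0.777 at 16 per arm and 0.813 at 17, so 17 reproduces. This calculation does not depend on how allocation is concealed.

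**2. Predictability.** Block size is not in the documents. Assume complete 1:1 blocks of fixed size 2h, known to the enroller, with all past allocations known.

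- Share certain in advance (one arm already used up): 1/(h+1).
- Expected correct guesses per block when the arm with more places left is always guessed: h + [4^h / C(2h,h) − 1]/2. Dividing by 2h gives the hit rate g.

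For a block of 4, h = 2: 1/3 = 33% are certain, and [2 + (16/6 − 1)/2]/4 = 2.833/4 = 71% are guessed.

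| Block size | Certain | Correct guesses (g) | 2g − 1 |
|---|---|---|---|
| 2 | 50% | 75% | 0.50 |
| 4 | 33% | 71% | 0.42 |
| 6 | 25% | 68% | 0.37 |
| 8 | 20% | 67% | 0.33 |
| 34 (single block) | 1/18 = 5.6% | 59% | 0.19 |

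Enumerating all sequences gives the same results for blocks of 2 to 8. For 34, 20,000 simulated sequences gave 5.5% and 59%. With no predictability, g is 50%.

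**3. From guessing to bias.** Suppose an enroller who expects TubeClear brings in subjects whose success chance is higher by d than those brought in when the other arm is expected. A fraction g of the TubeClear arm and 1 − g of the control arm are then favoured, so the arm difference shifts by [g − (1 − g)]d = (2g − 1)d. The documents give no d. For an assumed d of 10 to 20 points, with steering at every allocation, the shift is 5 to 10 points for blocks of 2 and 1.9 to 3.7 points for one block of 34. The planned difference is 95 − 50 = 45 points.

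**4. Fit to 34.** The remainder of 34 is 0 for blocks of 2, 2 for blocks of 4, 4 for blocks of 6 and 2 for blocks of 8. Of these, only blocks of 2 guarantee 17:17, and they are the most predictable. Mixed sizes can also fit, for example one block of 4 and five of 6 (4 + 30 = 34).

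**5. Cost of unequal arms.** The calculation in step 1 gives power of 0.863 and 0.852 for TubeClear:control of 16:18 and 18:16, and 0.827 and 0.846 for 15:19 and 19:15, against 0.813 at 17:17. The apparent gains come from the discreteness of Fisher's test. Power is not lost.

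**6. Order of steps.** Section 3.4.2 bars enrolment unless all criteria are met, and Section 3.2 opens the envelope after enrolment. Together they imply that length is known first. The Phase IIB list in Section 4.2 does not follow that order. The sections need to be reconciled.

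**The case against.** The plan has real safeguards. The sponsor generates the list. Envelopes are individual, sealed and opaque, and are opened after consent and enrolment. A reader might infer that staff can see the next allocation. The documents do not support that: it would need a breached envelope or a list in the team's hands, and responsibility for maintaining the sequence may mean only keeping the envelopes. The envelopes do not, however, prevent deduction from earlier allocations.

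A reader might also take it as stated that the same people screen, consent and hold the sequence. The Study Team is not defined. The overlap is an inference from Sections 9.1.2, 9.6 and 9.7, though a plausible one, since no separate group is described.

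Nor is lack of blinding the plan's only reason for blocking, because the full sentence names arm balance as the aim. That aim is legitimate; the clause on blinding is what does not follow.

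Finally, the mechanism can be called speculative. Occlusion is defined by an identified clog or a pump alarm (Section 3.1.1), with no hardness grade before treatment, and nothing suggests that attending physicians know the block size. That stands as a limit on how large d could be. But staff collect information on the clog and on what was given through the tube beforehand (Section 5.1.1), and a child may be enrolled up to three times (Section 3.1.1), so they are not without clues.

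**Conclusion.** The concern holds as a weakness in allocation concealment that should be corrected. In an open-label, single-site comparison of 34 with permuted blocks, the plan protects against viewing the next allocation but describes nothing that prevents its prediction: no withheld or varying block size, and no custodian outside enrolment. Envelope numbering and an envelope log are also not described.

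Assuming fixed, known blocks, certain allocations range from about 5.6% to 50% and correct guesses from 59% to 75%. Both would be lower if sizes vary and are withheld. These figures do not show that the endpoint would be biased; any shift depends on d, for which the documents give no value. Separately, the Phase IIB list in Section 4.2 leaves open that tube length, an eligibility fact, is settled after the arm is known.

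**What to change.** Amend Sections 3.2, 4.2 and 9.1.1, and align Section 3.1.2 with them:

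- **Blocks.** Use randomly varying block sizes that are not disclosed to enrolling staff.
- **Custody.** Have the list held, and each allocation released, by someone outside the enrolling team. The REDCap project in Section 9.5 could do this if its set-up allows. Otherwise, use existing staff who do not enrol, with sequentially numbered and logged envelopes.
- **Timing.** Release an allocation only after consent, all eligibility criteria, and tube length and type are recorded, in the same way for both arms.

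The cost is a regenerated list, a named custodian and a short pre-allocation record. The sample size stays at 34. Arms may differ from 17 each by one or two, which by the check above does not take power below 0.80. If exact balance is wanted, mixed sizes that sum to 34 can provide it.
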